**Table 7-2 Guideline on management of infusion-related reactions and systemic hypersensitivity reactions**

NCI-CTCAE Grade	Treatment Modification for KN046
Grade 1 – mild Mild transient reaction; infusion interruption not indicated; intervention not indicated.	Decrease the KN046 infusion rate by 50% and monitor closely for any worsening.
Grade 2 – moderate Therapy or infusion interruption indicated but responds promptly to symptomatic treatment (e.g., antihistamines, NSAIDs, narcotics, i.v. fluids); prophylactic medications indicated for ≥ 24 hours.	Stop KN046 infusion. Resume infusion at 50% of previous rate once infusion-related reaction has resolved or decreased to at least Grade 1 in severity, and monitor closely for any worsening.  Once the KN046 infusion rate has been decreased by 50% due to an infusion-related reaction, it must remain decreased for all subsequent infusions. At next cycle, a premedication regimen of diphenhydramine 25~50 mg IV, cimetidine 300 mg IV and acetaminophen 650 mg po is mandatory 30 to 60

NCI-CTCAE Grade	Treatment Modification for KN046
	
minutes prior to each dose of KN046). If subject developed symptomatic bronchospasm, premedication with montelukast (10 mg PO) is mandatory as part of premedication regimen mentioned above. At the discretion of investigator, premedication of corticosteroid can also be considered. If a subject has a recurrence of <math>\geq</math>grade 2 infusion related reactions despite the premedications as well as decreased infusion rate, the subject should be withdrawn from KN046 treatment.
 
It's also suggested to the investigator discuss with the allergist locally.

Grade 3 or Grade 4 – severe or life-threatening Grade 3: Prolonged (e.g., not rapidly responsive to symptomatic medication and/or brief interruption of infusion); recurrence of symptoms following initial improvement; hospitalization indicated for clinical sequelae. Grade 4: Life-threatening consequences; urgent intervention indicated.	Stop the KN046 infusion immediately and disconnect infusion tubing from the subject. Subjects have to be withdrawn permanently from KN046.
Note: once the subject develops infusion related reactions, additional appropriate medical therapy may include but is not limited to: IV fluids, antihistamines, NSAIDS, acetaminophen and narcotics. Increase monitoring of vital signs as medically indicated until the subject is deemed medically stable in the opinion of the investigator. If symptoms resolve within one hour of stopping drug infusion, the infusion may be restarted at 50% of the original infusion rate (e.g. from 100 mL/hr to 50 mL/hr). Otherwise dosing will be held until symptoms resolve and the subject should be premedicated for the next cycle.	

i.v.=intravenous, NCI-CTCAE=National Cancer Institute-Common Terminology Criteria for Adverse Event, NSAIDs=nonsteroidal anti-inflammatory drugs.

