## 1. Protocol Summary

Full Title:	Phase II study of KN046 in patients with thymic carcinoma who failed immune checkpoint inhibitors
Short Title:	KN046 in thymic cancer with prior IO
Clinical Phase:	II
Principal Investigator:	[name] PhD
Study Description:	This study will assess the safety and efficacy of KN046 in patients with advanced thymic carcinoma who progressed after prior treatment with immune checkpoint inhibitors
Sample Size:	N= 29
Enrollment:	This study will enroll 29 patients
Study Population:	These are patients with advanced thymic carcinoma who have had progression after treatment with chemotherapy and an immune checkpoint inhibitor. They have no prior or current history of autoimmune disorders.
Enrollment Period:	24 months
Study Design:	Open-label, single arm, single center non-randomized Phase II study to investigate the efficacy and safety of KN046 in patients with advanced thymic carcinoma who have progressed on prior immune checkpoint inhibitor therapy. Subjects will be treated with KN046 5 mg/kg q2wk
Description of Sites/ Facilities Enrolling	
Participants:	Weill Cornell Medicine/New York Presbyterian Hospital
Study Duration:	7/2024
Participant Duration:	24 months
Study Agent/Device Name	KN046
Intervention Description:	KN046 will be given intravenously at 5 mg/kg every 2 weeks. A cycle is defined as 2 treatments (28 days). Treatment will be until progression or excessive toxicity for up to 2 years.
Primary Objective:	To evaluate the anti-tumor activity of KN046 in subjects with thymic carcinoma as measured by overall response rate
Secondary Objectives:	To assess the safety and tolerability of KN046
Exploratory Objectives:	To explore the association of biomarkers (including, but not limited to, PD-L1 expression, tumor immune microenvironment determined by multiplex IHC, tumor mutational burden (TMB), T-cell inflamed gene expression profile (GEP)) and clinical efficacy parameters
	To characterize the safety laboratory results (AChR autoantibody and CPK) and the occurrence of adverse events of interest
Endpoints:	Response rate, progression-free survival, overall survival

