**KN046 Q2W schedule**

Full profiles shown only after Cycle 1 and Cycle 6 doses; trough concentrations shown for Cycles 2-5.

[figure not shown]
● Median of simulations  
■ 90% prediction interval (bounded by 5th and 95th percentile of simulations)

Full profiles shown only after Cycle 1 and Cycle 6 doses; trough concentrations shown for Cycles 2-5.

[figure not shown]
● Median of simulations  
■ 90% prediction interval (bounded by 5th and 95th percentile of simulations)

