- 19 Tumor assessment will be performed using PET/CT at baseline, at time of best response, and when clinically indicated. CT scans of chest, abdomen and pelvis (Chest CT and MRI of Abdomen and Pelvis also acceptable) are also required at baseline, every 2 cycles (8 weeks) for the first year, then every 4 cycles (16 weeks) for the second year. Screening tumor assessment should be performed within 28 days of first trial treatment in order to document baseline status of tumor disease using RECIST 1.1 target and non-target lesions. During treatment period, the tumor assessment visit time window is  $\pm$ 7 days. CT or MRI scan (if MRI is used, CT of chest is mandatory) should always be used in the same modality as the screening period. If a tumor response is documented during the study, confirmation of the response should be performed according to RECIST 1.1, preferably at the regularly scheduled 8-week assessment interval, but no sooner than 4 weeks and no later than 8 weeks after the initial documentation of CR or PR. Confirmation of PR/CR can be done at an assessment later than the next assessment after the initial documentation of PR/CR. If disease progression is documented, confirmation of PD is required, preferably at 8-week assessment interval (but no sooner than 4 weeks and no later than 8 weeks). Tumor assessment will continue until confirmed disease progression per RECIST 1.1, start of new anti-cancer therapy, or withdrawal of informed consent, whichever comes first. If treatment discontinuation is due to reasons other than RECIST 1.1 defined progressive disease, tumor assessment should continue until RECIST 1.1 defined progressive disease, start of new anti-cancer therapy, or withdrawal of informed consent, whichever comes first;
- 20 Brain CT/MRI scan (either, with contrast preferred) is required at screening if not performed within the previous 42 days prior to first trial treatment. During treatment period, brain CT/MRI scan should be done if clinically indicated by development of new specific symptoms;
- 21 Each KN046 will be administered intravenously over at least 90 minutes (90-120 minutes). After the completion of KN046 infusion, subject should be observed at site for at least 2 hours.
- 22 If necessary to confirm postmenopausal status
- 23 Day 1 of each cycle only
- 24 To occur on Day 1 of odd Cycles only
- 25 If ANA or ENA positive, rheumatologic workup indicated.
- 26 Will only repeat ctDNA if genetic alteration detected at baseline.

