#### **6.1.2.2 Day 15 of each Cycle**

- Concomitant medications and procedures
- Adverse Event Assessment
- Full physical exam
- Body Weight
- Tumor Imaging (if applicable)
- Vital Signs
- ECOG Performance Status
- CBC, metabolic panel, CPK, troponin
- Coagulation tests (if clinically indicated)
- Urinalysis (as defined in SOA)
- T3, FT3, FT4, TSH (as defined in SOA)
- CRP, IL-6 (as clinically indicated)
- Brain CT/MRI (as clinically indicated)
- For C2D15 only: Cardiac Ultrasonography

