#### **7.9 Assessment of investigational medicinal product compliance**

In this study, subjects will receive the KN046 at the study site. Well trained medical staff will monitor and perform administration of KN046. Details of each administration of KN046 including the date, time, and dose will be recorded on the eCRF. The Investigator will make sure that the information entered onto the eCRF regarding administration is accurate for each subject. Any reason for noncompliance should be documented.

Noncompliance is defined as a subject missing > 3 cycles or 12 weeks of KN046 for nonmedical reasons. Should these situations occur, the subject should be withdrawn from KN046 treatment (See Section **Error! Reference source not found.**).

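### Table 7-2 starts mandatory premedication at the next 28-day cycle, so after a Day 1 Grade 2 infusion reaction the Day 15 infusion is given outside the mandate

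*Combined protocol and SAP*

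**What the plan says.** For a Grade 2 infusion-related reaction, Table 7-2 gives two rules for later dosing. The infusion rate is halved, and "it must remain decreased for all subsequent infusions". The next sentence deals with premedication: "At next cycle, a premedication regimen of diphenhydramine 25~50 mg IV", together with cimetidine and acetaminophen, is mandatory 30 to 60 minutes before each dose. The row then withdraws a patient who has another reaction of Grade 2 or higher despite both the premedication and the slower rate.

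Two other places set premedication by cycle. The Note under Table 7-2, for reactions that do not settle within an hour, says "the subject should be premedicated for the next cycle". Section 7.5.1, on continuing after a hypersensitivity reaction, ties prophylaxis to subsequent dosing cycles.

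The Protocol Summary contains the only stated definition: "A cycle is defined as 2 treatments (28 days". Section 6.1.2.2 lists a second infusion visit under "Day 15 of each Cycle". Footnote 19 of the Schedule of Assessments equates two cycles with eight weeks, "every 2 cycles (8 weeks) for the first year". Section 7.9 follows the same count: "Noncompliance is defined as a subject missing > 3 cycles or 12 weeks of KN046 for nonmedical reasons".

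The pharmacokinetic simulation in Section 3.3 uses the word differently. Under the every-two-weeks schedule it says "Full profiles shown only after Cycle 1 and Cycle 6 doses; trough concentrations shown for Cycles 2-5", which appears to mean one dose per cycle.

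**The concern.** Premedication after a Grade 2 reaction is meant to protect the next exposure. If *cycle* carries its defined meaning, the mandate reaches that exposure when the reaction fell on Day 15, but misses it when the reaction fell on Day 1. The protocol gives no reason for treating the two patients differently.

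Two things are at stake. One is prevention: at the first re-exposure after a Day 1 reaction, premedication is left to the investigator although the row otherwise calls it mandatory. The other is the withdrawal criterion. It needs a recurrence despite premedication, so a Grade 2 recurrence on an unpremedicated Day 15 does not meet it, and the patient could be dosed again under this row.

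**Working it through.** **Inputs.** Infusions every 14 days (Protocol Summary; Section 7.2). Two infusions per cycle, on Days 1 and 15 (Protocol Summary; Sections 6.1.2.1 and 6.1.2.2).

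**The plan's own figure.** Cycle length = 2 infusions × 14 days = 28 days, as stated. Cross-checks: footnote 19 gives 8 weeks ÷ 2 cycles = 56 ÷ 2 = 28 days; Section 7.9 gives 12 weeks ÷ 3 cycles = 84 ÷ 3 = 28 days. The definition is used consistently in the visit, imaging and compliance rules.

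**Infusion calendar.** Infusions in cycle *c* fall on study days (*c* − 1) × 28 + 1 and (*c* − 1) × 28 + 15, that is, 1, 15, 29, 43 and so on.

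**When the mandate starts, by day of reaction.**

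| Grade 2 reaction on | Next infusion | Start of next cycle | Infusions before the mandate starts |
|---|---|---|---|
| Day 1 | Day 15 (15 − 1 = 14 days later) | Day 29 (29 − 1 = 28 days later) | 1 (Day 15) |
| Day 15 | Day 29 (29 − 15 = 14 days later) | Day 29 (14 days later) | 0 |

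The same pattern holds in every later cycle, since each repeats the 28-day layout. It assumes the patient stays on the two-weekly schedule.

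**Does other text close the gap?**
- The requirement to premedicate before each dose stands in the same sentence, after the words that set the start. It fixes the frequency once the rule is running and does not move the start forward.
- The Note and Section 7.5.1 also count in cycles.
- The rate rule counts in infusions, so it does reach Day 15, but it concerns rate only.
- No other text requires premedication at the next infusion within a cycle.

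**With the rule stated in infusions.** After a Day 1 reaction the mandate starts on Day 15, 14 days later, with no infusion uncovered. After a Day 15 reaction the date does not change.

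**The case against.** The strongest reply is that *cycle* in these passages means a dosing occasion. Section 7.5.1 asks for prophylaxis 30 to 45 minutes before the administration of a cycle, and one administers a dose, not a 28-day period. Read with 28-day cycles, that section would premedicate only Day 1 infusions and never Day 15, against the before-each-dose wording in Table 7-2. The simulation text already uses the word for a single dose, and the neighbouring rate rule speaks of infusions. On this reading the passages agree and nothing is missed.

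Most of that stands as evidence of intent: the next infusion was probably meant. It does not settle the instruction, because it asks site staff to set aside the only stated definition of a cycle, one the visit, imaging and compliance rules all follow.

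A second reply is that little risk remains. Section 2.4.1.2 calls this material suggested guidance and Table 7-2 is titled a guideline. At Day 15 the halved rate is compulsory, Section 7.5 requires two hours of observation with resuscitation equipment at hand, Section 7.4.1 permits premedication, and the row suggests consulting an allergist. This is why the effect is small. It does not remove the point, since the row itself makes premedication mandatory.

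A reader might also infer that the Day 15 dose is omitted. Nothing in the row says so: the infusion goes ahead, and only the mandate passes over it.

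**Conclusion.** The point holds as a wording gap in an operative safety rule. Under the stated definition of a cycle, one infusion, Day 15, falls outside the premedication mandate for each patient whose Grade 2 reaction occurs on a Day 1 dose. A Grade 2 recurrence there, if unpremedicated, would not meet the row's withdrawal criterion. Grade 3–4 reactions still require permanent withdrawal, Grade 1 carries no premedication mandate in the table, and withdrawal for unacceptable toxicity under Section 8.1 and the Stopping Rules remains open. So one should not infer that a patient who reacts again on Day 15 must continue.

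The number of affected patients cannot be estimated. A reader might try the phase I tables: at 5 mg/kg every two weeks, reactions of any grade were 4/30 in the Australian trial and 6/45 in the Chinese trial, 10/75 together. Removing Grade 3 or higher (1/45 in the Chinese trial; 0/30 or 1/30 in the Australian trial, where the safety summary and Table 2-3 differ) leaves 9/75 or 8/75, and 29 × 9/75 = 3.5 or 29 × 8/75 = 3.1 patients. That is neither an estimate of those affected nor a ceiling on them. It pools Grade 1 with Grade 2 and all dose days, and carries over a point estimate from other populations. The documents give no Grade 2 count and no timing by dose day, and the number here could be zero.

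The conclusion rests on applying the stated definition literally. That the next infusion was intended is an inference, though a likely one. There is no bearing on the two-stage design, the endpoint or the analysis.

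**What to change.** Change three phrases:
- **Table 7-2, Grade 2 row:** replace *At next cycle* with *Starting with the next infusion*, keeping the requirement that follows to premedicate before each dose.
- **Table 7-2, Note:** end the premedication instruction with *for the next infusion* instead of *for the next cycle*.
- **Section 7.5.1:** replace the words from *the administration of* through *dosing cycles* with *the next and every subsequent infusion*.

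If the Pharmacy Manual repeats the rule, change it there too. While these sentences are open, reconcile the premedication lead time, which is 30 to 45 minutes in Section 7.5.1 and 30 to 60 minutes in Table 7-2.

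The only clinical cost is one earlier premedication per affected patient. Sample size, endpoint and analysis are untouched.

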## 7.6 Packaging and labeling of the investigational medicinal product

The Sponsor's Clinical Trial Supply Chain department will supply the investigational medicinal product, KN046.

Packaging and labeling of KN046 will be in accordance with applicable regulatory requirements and Good Manufacturing Practice guidelines. KN046 will be packed in boxes containing a suitable number of vials. The information on the KN046 will be in accordance with approved submission documents. KN046 will be shipped in transport cool container (2°C to 8°C), according to the storage and shipping conditions. Shipments will be monitored with temperature control devices.

## 7.7 Preparation, handling and storage of the investigational medicinal product

KN046 drug product must be diluted with sterile 5% dextrose in water supplied in an infusion bag. Detailed information on preparation of the dilutions and subsequent administration will be provided in the Manual of Preparation.

The study drug must be stored at 2°C to 8°C until use, with a temperature log maintained daily. The

study drug must be stored carefully and safely from other drugs that can only be accessed by investigators and authorized site personnel.

### **7.8 Investigational medicinal product accountability**

The Investigator is responsible for ensuring accountability for KN046, including reconciliation of drugs and maintenance of drug records.

Upon receipt of study drugs, the Investigator (or designee) will check for accurate delivery and acknowledge receipt by signing (or initialing) and dating the documentation provided by the Sponsor and returning it to the Sponsor. A copy will be retained for the Investigator Site File.

Dispensing of study drugs will be carefully recorded on the appropriate drug accountability forms provided by the Sponsor and an accurate accounting will be available for verification by the Clinical Research Associate (CRA) (or equivalent) at each monitoring visit.

Study drug accountability records will include:

- Confirmation of study drug delivery to the study site;
- The inventory at the site of study drug provided by the Sponsor and prepared at the site;
- The use of each dose of study drug by each subject;
- Destruction of unused study drug;
- Dates, quantities, batch number, expiry dates and formulation, as well as the subjects' Study Identifier Numbers.

The investigator should maintain records that adequately document:

- That the subjects were provided the doses specified by the Clinical Trial Protocol / Amendment(s);
- That all study drug provided by the Sponsor was fully reconciled.

Unused study drug must not be discarded or used for any purpose other than this study. Any study drug that has been dispensed to a subject must not be re-dispensed to a different subject. The CRA will periodically collect the study drug accountability forms and will check all returns (both unused and used containers) before authorizing their destruction by the site.

At the conclusion or termination of this study, site personnel and the CRA will conduct a final product supply inventory on the Drug Accountability Forms and all unused containers will be destroyed. Instructions for destruction of study drug will be provided to the site. The CRA will be supplied with a copy of the Drug Accountability Forms for filing. This documentation must contain a record of clinical supplies used, unused and destroyed, and shall include information on:

- All administered units;
- All unused units;
- All destroyed units (during the study);
- All destroyed units at the end of the study;
- Date(s) of destruction(s);
- Name and signature of the Investigator/pharmacist.

In addition, it must be ensured at each study site that the study drug **MUST NOT BE** used:

- After the expiry date;
- After the retest date, unless the study drug is reanalyzed and its retest date extended.

This is to be closely monitored by the CRA.

#### **7.9 Assessment of investigational medicinal product compliance**

In this study, subjects will receive the KN046 at the study site. Well trained medical staff will monitor and perform administration of KN046. Details of each administration of KN046 including the date, time, and dose will be recorded on the eCRF. The Investigator will make sure that the information entered onto the eCRF regarding administration is accurate for each subject. Any reason for noncompliance should be documented.

Noncompliance is defined as a subject missing > 3 cycles or 12 weeks of KN046 for nonmedical reasons. Should these situations occur, the subject should be withdrawn from KN046 treatment (See Section **Error! Reference source not found.**).

#### **7.10 Duration of Follow Up**

Subjects will be followed for 2 years after removal from study or until death, whichever occurs first. Subjects removed from study for unacceptable adverse events will be followed until resolution or stabilization of the adverse event.

#### **7.11. Measures to Minimize Bias: Randomization and Blinding**

This is an open-label trial. There is no blinding.

### **8. Study Intervention Discontinuation and Participant Discontinuation/Withdrawal**

Participants are free to withdraw from participation in the study at any time.

#### **8.1 Criteria for subject withdrawal**

A subject must be withdrawn from KN046 in the event of any of the following:

- Confirmed PD per RECIST 1.1 and the investigator consider that continuing KN046 treatment will not benefit (note: subject receiving KN046 may continue past the initial determination of PD if the subject meets the criteria of clinically stable);
- Significant clinical deterioration (clinical progression) is defined as new symptoms that are deemed by the investigator to be clinically significant or significant worsening of existing symptoms;
- Therapeutic failure requiring urgent additional anticancer drug;
- Unacceptable toxicity (if a subject does not occur RECIST 1.1 defined confirmed PD, the subject will be asked to continue tumor assessment until RECIST 1.1 defined PD is confirmed);
- Occurrence of pregnancy;
- Use of a nonpermitted concomitant drug as defined in Section 7.4.2 where the predefined consequence is withdrawal from KN046;

- Withdrawal of the subject's consent to continue KN046 (if a subject withdraws consent, the subject will be asked to continue tumor assessments if RECIST 1.1 defined confirmed PD does not occur);
- Noncompliance.
- Withdrawal of the subject's consent. If the subject withdraws consent, it must be clearly stated if the subject is also withdrawing their consent from the post-treatment follow-up assessments;
- Participation in any other therapeutic study during the Treatment Phase of this study; however, subjects will continue to be followed for new anticancer therapy and for survival;
- Lost to follow-up.

In case of withdrawal from the study, the assessment schedule for end-of-treatment visit should be performed if possible and focus on the most relevant assessments. Subjects will be asked to continue safety and long-term follow-up, which includes the collection of data on survival and subsequent anticancer therapy.

The investigator must determine the primary reason for the subject's withdrawal as completely and accurately as possible. The reason for participant discontinuation or withdrawal from the study will be recorded in the medical record and RedCap.

